3.3.4.2 CCI

3.3.4.3 CCI

3.3.4.4 CCI

3.3.5 Safety endpoints

3.3.5.1 Adverse events

An adverse event is the development of any untoward medical occurrence in a subject or clinical study subject administered a medicinal product and which does not necessarily have a causal relationship with this treatment. An AE can therefore be any unfavourable and unintended sign

(e.g., an abnormal laboratory finding), symptom (e.g., nausea, chest pain), or disease temporally associated with the use of a medicinal product, whether or not considered related to the medicinal product. The term AE is used to include both serious and non-serious AEs and can include a deterioration of a pre-existing medical occurrence. An AE may occur at any time, including run-in or washout periods, even if no study treatment has been administered.

Serious adverse events (SAEs) will be collected from time of signature of informed consent (either the brief, pre-screening ICF or the full, screening ICF), throughout the treatment period and including the follow-up period. All non-serious AEs will be recorded from time of first dose of study treatment, throughout the treatment period and including the follow-up period. Adverse events (AEs) will be coded with the most up to date MedDRA version. For any additional details on AE reporting please refer to the study protocol.

The AEs are assigned to the analysis phases described in section [3.1.3](#), based on the AE start date as follows:

- If the AE start date is before the first dose of treatment date, then the AE is assigned to the pre-treatment phase,
- If the AE start date is on or after the first dose of treatment date through 28 days after last dose of treatment (inclusive), then the AE is assigned to the on-treatment phase,
- If the AE start date is more than 28 days after last dose of treatment, then the AE is assigned to the follow-up phase.

If the start date of an AE is completely missing, the AE is assigned as follows:

- If the AE end date is known and is before the first dose of treatment date, then the AE is assigned to the pre-treatment phase,
- If the AE end date is completely missing or if the AE end date is on or after the first dose of treatment date no assignation can be done.

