The study day of start of the AE is calculated as the start date of the AE - date of the first dose of treatment +1 for AE started on or after day 1 and as the start date of the AE - date of the first dose of treatment for AE started before day 1. Study day of start of AE is calculated for complete dates only. Imputed dates should not be used. If one of the dates is missing or partially missing, the study day of start of the AE is missing.

All the AEs in the on-treatment and follow-up phases are considered treatment emergent adverse events (TEAEs).

The duration of AE is calculated as the end date of the AE – start date of the AE +1. Duration is calculated for complete dates only. Imputed dates should not be used. If one of the dates is missing or partially missing, the duration is missing.

The analysis will be based on as-treated population.

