The following summary tables will be presented by PT:

- The number and percentage of subjects with most common AEs (frequency of >5%). Most common should be defined according to % in any of the treatment groups.
- The number and percentage of subjects with any AEs by maximum reported intensity.
- The number and percentage of subjects with any AEs and investigator's causality assessment. If a subject has multiple events in the same PT, the event with the strongest relationship will be counted.

Where number of subjects with AEs are summarized by system organ class (SOC) and/or preferred term (PT), subjects with multiple events in the same SOC/PT are counted only once in that SOC/PT. Subjects with events in more than one SOC/PT are counted once in each of those SOCs/PTs.

Additionally, the following tables will be presented:

- The number and percentage of subjects with non-serious AEs occurring with a frequency > 5.0% in any treatment group for each SOC and PT.

This table will be produced as a separate pdf output to meet clinical trial transparency requirements and not for inclusion in the clinical study report (CSR). It will be delivered at the same time as the CSR outputs.

Key subject information for subjects with:

- AEs with outcome of death
- SAEs
- AEs leading to discontinuation of study treatment

The durations reported in these tables, will be derived only for fully completed dates as below:

- Time from first dose of treatment to AE (in days) will be calculated as the AE start date minus date of first dose +1.
- Time from first dose to death (in days) will be calculated as the date of death minus date of first dose +1.
- The same approach will be used for deriving time from start of treatment to AE becoming serious or discontinuation.
- Time from last dose prior to AE start and last dose prior to death will be calculated as the date of death minus the date of last dose prior to AE/death +1.

A listing will be provided for all the AEs regardless of the analysis phases for all subjects included in the as-treated population.

All analyses will be conducted in IDMC reports and at final analysis.

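### SAP 4.2.10.7 derives the time from the last dose before AE start using the date of death, so it has no value in survivors and is too long whenever onset precedes death

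*SAP*

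**What the plan says.** SAP section 4.2.10.7 (Adverse events) plans key subject information for three groups: fatal AEs, SAEs, and "AEs leading to discontinuation of study treatment". It then sets a condition: "The durations reported in these tables, will be derived only for fully completed dates as below". The rules that follow are these:

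- First dose to AE: "Time from first dose of treatment to AE (in days) will be calculated as the AE start date minus date of first dose +1".
- First dose to death: "Time from first dose to death (in days) will be calculated as the date of death minus date of first dose +1".
- Start of treatment to an AE becoming serious, or to discontinuation: by the same approach.
- Last dose, for both the AE and death: a single rule, under which both durations "will be calculated as the date of death minus the date of last dose prior to AE/death +1".

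The section closes by assigning all these analyses to both the IDMC reports and the final analysis. No other section of the SAP gives a rule for the time from last dose to AE onset.

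**The concern.** The first-dose durations have separate rules, each ending on the date of the event it names. The last-dose durations were merged into one sentence, and the AE start date dropped out. A programmer who follows the text will subtract the last dose before the AE from the date of death.

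Two of the three tables, SAEs and AEs leading to discontinuation, can include people who survive and so have no date of death. Where the participant does die, a number is printed that measures something other than dose to onset.

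The interval is worth having right. Dosing is every 4 weeks (SAP 3.4), so time since first dose does not show how close an event was to the most recent injection. What is at stake is the accuracy of a descriptive column that the IDMC and readers of the study report will see.

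**Working it through.** The SAP states no figure for this duration, so there is none to reproduce. The check applies the written rule literally and compares it with the rule that parallels the SAP's own first-dose bullet.

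**Inputs.** L is the study day of the last dose before the AE, S the AE start day, and D the day of death. The dose days used (29, 85, 113, 197, 225) are from the schedule in SAP 3.4. The onset and death days are assumptions chosen to cover the possible situations.

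**Formulas.**

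- SAP rule as written: D − L + 1
- Dose to onset, mirroring the first-dose rule: S − L + 1
- Difference: (D − L + 1) − (S − L + 1) = D − S

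The excess is therefore exactly the days from onset to death. It is zero when S = D, and there is no result when D does not exist.

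| Case | L | S | D | SAP rule | Dose to onset | Excess |
|---|---|---|---|---|---|---|
| (a) Fatal AE, onset before death | 85 | 100 | 120 | 120 − 85 + 1 = 36 | 100 − 85 + 1 = 16 | 20 |
| (b) Fatal AE, onset on day of death | 85 | 100 | 100 | 100 − 85 + 1 = 16 | 100 − 85 + 1 = 16 | 0 |
| (c) Non-fatal SAE, participant survives | 29 | 40 | none | not calculable | 40 − 29 + 1 = 12 | – |
| (d) Non-fatal SAE, participant dies later | 29 | 40 | 200 | 200 − 29 + 1 = 172 | 40 − 29 + 1 = 12 | 160 |
| (e) Fatal AE after the final dose | 225 | 230 | 300 | 300 − 225 + 1 = 76 | 230 − 225 + 1 = 6 | 70 |

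For scale, scheduled doses are 28 days apart (for example, 113 − 85 = 28). Case (d) matters most in kind: the cell is filled rather than blank, and the number relates to a later death and not to the event on that row.

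The death duration is sound as written. In case (a), if the last dose before death was on Day 113, the time from that dose to death is 120 − 113 + 1 = 8. In case (d), with a last dose on Day 197, it is 200 − 197 + 1 = 4.

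**What does not depend on this rule.** Phase assignment in SAP 3.3.5.1 uses AE onset and last dose: "If the AE start date is more than 28 days after last dose of treatment, then the AE is assigned to the follow-up phase". AE study day counts from the first dose: "The study day of start of the AE is calculated as the start date of the AE - date of the first dose of treatment +1". Treatment-emergent status follows from the phase. None of these uses the date of death.

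**The case against.** The best defence is a different reading. The bullet never says that the first interval ends at AE onset. It could mean two intervals that both end at death, one from the last dose before the AE and one from the last dose before death. That fits the single leading date, and on it the table of fatal AEs is coherent. This is a fair reading, but it does not rescue the rule: survivors in the other two tables still get no value, and the SAP then defines no dose-to-onset interval at all.

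It can also be said that a duration undefined for survivors is not in itself an error, since time from first dose to death is undefined for them too. That is true of a duration to death. It is no defence for one tied to AE start. The table shells might show which columns appear in which table, but they are not among the documents, and the written rule is what stands.

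Three stronger conclusions are tempting, and the documents do not support them:

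- *The value is missing for every non-fatal AE.* It is missing only if the participant does not die; case (d) gives a wrong value instead.
- *The value is wrong for every fatal AE.* It is right when onset and death fall on the same day, as in case (b).
- *The assessment of causality is undermined.* Causality is the investigator's yes/no judgement (protocol 8.3.3) and is not derived from this column. Bleeding and injection site reactions have their own incidence tables. Events that are neither serious nor lead to discontinuation do not reach the three tables. AEs are listed (SAP 4.2.10.7) and dose administration is listed at final analysis (SAP 4.2.5.2), so the interval can be recovered by hand at that stage.

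**Conclusion.** Wrong as written, and minor. Taken literally, the rule gives no duration for any AE in a participant who does not die. In a participant who dies, it overstates dose to onset by the date of death minus the AE start date: 20, 70 and 160 days in the illustrations where onset came first, and 0 where it did not.

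The damage stops at descriptive duration columns in the three key-subject tables. AE incidence and all efficacy analyses are unaffected, as are phase and treatment-emergent status.

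This rests on two things: that the sentence is programmed as it reads, and that the quantity wanted is time from last dose to AE start, as the neighbouring first-dose rule suggests. The documents give no number of deaths or SAEs, so the count of affected records cannot be stated.

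**What to change.** Replace the last duration bullet in SAP 4.2.10.7 with two:

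- *Time from last dose prior to AE = AE start date minus date of last dose prior to AE start + 1.*
- *Time from last dose prior to death = date of death minus date of last dose prior to death + 1.*

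This keeps the SAP's +1 convention and mirrors its first-dose rules. The programs and any shell footnotes for the three tables should be checked against the new text. The dates needed (AE start, dosing and death) are already collected, so the cost is one edited sentence and a programming check. There is no downside.

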ADA	
 Treatment of participants with mAbs carries the theoretical risk of induction of ADA. 	
 Participants will be assessed for the development of ADA (Section 8.5.2).
Study procedures		
Injection site reactions	
 As with any exogenous protein substance, injection site reactions may be seen as a response to SC injection of MEDI6570. No instances of injection site reactions were reported in monkeys during toxicity studies with MEDI6570. CCl [REDACTED] 	
 Participants receiving SC injections of study intervention will be monitored closely for the development of injection site reactions (Section 8.2.5.3)

Table 6 Risk Assessment

Potential Risk of Clinical Significance	Summary of Data and/or Rationale for Risk	Mitigation Strategy
CTA scan	
Potential clinical consequences of undergoing a CTA scan include, as follows:
 
 • Radiation exposure • Reactions to iodinated contrast • Renal impairment due to contrast administration • Detection of incidental findings that may require assessment 	
 • Radiation reduction technologies, including prospective ECG-triggering and iterative reconstruction, allow CTA scans to be performed at low radiation doses (Chen et al 2013, Hou et al 2014, Meyersohn et al 2017, Schermund et al 2017). Radiation reducing image acquisition techniques will be used (Section 8.1.1) and the anticipated median (range) radiation exposure per CTA imaging time point is 6 (3-10) mSv. • Risks of renal impairment will be minimized by excluding participants with clinically significant renal disease from CTA scanning (Section 8.1.1). • For each CTA scan, critical alert findings of clinical importance will be interpreted locally at the site to permit appropriate assessment and treatment (Section 8.1.1).

ADA, anti-drug antibody(ies); AE, adverse event; CTA, computed tomography angiography;

ECG, electrocardiogram; Ig, immunoglobulin; CCI

mAb, monoclonal antibody; mSv, millisievert; NSAID, Non-steroidal anti-inflammatory drug; PPI, Proton Pump Inhibitors; SC, subcutaneous(ly)

More detailed information about the potential risks of MEDI6570 can be found in the IB.

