The study will be conducted at approximately 70 to 100 study sites globally. The COVID-19 pandemic may continue to affect different geographic regions differently, having an unpredictable impact on study enrollment; therefore, a more accurate estimation of the number of countries and study sites that may be included globally is challenging.

Participants will be enrolled in the study for up to approximately 12 months, comprising an optional, pre-screening period of up to 42 days (6 weeks), a screening and baseline imaging period of up to 42 days (6 weeks), an intervention period of 225 days (31 to 32 weeks), and a follow-up period of 100 days (approximately 14 weeks; [Figure 1](#)). Following screening and confirmation of eligibility, participants will undergo an echocardiogram and CTA scan before randomization. The first dose of study intervention will be administered on Day 1 (Visit 3), after randomization. During the follow-up period, participants will undergo an echocardiogram and CTA scan.

An independent DMC will review safety data from this study (Section [9.6](#) and [Appendix A 5](#)).

No formal interim analysis is planned. An analysis restricted to PK (serum MEDI6570 concentration) and CCI [REDACTED] data will be performed after approximately 80 participants have completed the Day 57 visit (Visit 6), to evaluate the PK data and the PK-PD relationship. Non-study personnel who have no other involvement in the study will perform this evaluation. These PK and PD data will be reviewed in conjunction with the safety data by the independent DMC.

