 - (a) AST $> 2.0 \times$ ULN.
 - (b) ALT $> 2.0 \times$ ULN.
 - (c) TBL $> 1.5 \times$ ULN (unless due to Gilbert's syndrome).
 - (d) Platelet count < 100000 platelets/ μ l.
- 9 BP values at screening Visit 1:
 - (a) Systolic BP < 90 mmHg or > 180 mmHg.
 - (b) Diastolic BP > 100 mmHg.
 - (c) Participants who are excluded based on elevated BP may be rescreened following adequate treatment.

The eligibility assessment is based on measurements taken starting from after 5 minutes of rest; if the result is outside these limits, additional BP measurements can be taken over the following 5 minutes, ie, up to a total of 10 minutes of rest (repeated a maximum of 3 times). If the result is outside these limits during this period, the participant is considered a screen fail.

- 10 Participants with any of the following contraindications to CTA:
 - (a) eGFR < 50 mL/min/1.73 m² by the Chronic Kidney Disease Epidemiology Collaboration equation, or end stage renal disease treated with kidney transplant or renal replacement therapy.
 - (b) Allergy to iodinated contrast.
 - (c) History of contrast-induced nephropathy.
 - (d) Contraindication to nitroglycerin.
 - (e) Rapid heart rate that is uncontrolled by medical therapy.
 - (f) Inability to hold breath for at least 6 seconds.
- 11 Receipt of any investigational device or therapy within 6 months or 5 half-lives before screening (whichever is longer).
This criterion does NOT apply for inactive, non-replicating COVID-19 vaccines approved by Health Authorities or under emergency use authorization.
- 12 Planned participation in an additional investigational study of an intervention or biologic before the end of the follow-up period. Participation in observational studies or studies without investigational drugs or devices is allowed.
- 13 Participants who are legally institutionalized.
- 14 An employee or close relative of an employee of the sponsor, the CRO, or the study site, regardless of the employee or close relative's role.

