5.4 Screen Failures

Potential participants who are pre-screened and/or screened for the purpose of determining eligibility for the study, but are not randomly assigned in the study, are considered screen failures.

A minimal set of screen failure information is required to ensure transparent reporting of screen failure participants to meet the Consolidated Standards of Reporting Trials publishing requirements and to respond to queries from regulatory authorities. Minimal information includes demography, screen failure details, eligibility criteria, and any SAEs.

Rescreening

Participants who fail screening may be rescreened under the following circumstances:

- Eligible participants who exceed the 42-day pre-randomization window may be rescreened to determine eligibility before randomization and the Medical Monitor will decide whether screening laboratory evaluations should be repeated. If the screening assessments are not considered to be representative of the usual status of the health of the participant by the investigator, or if ≥ 1 exclusion criteria are considered temporary (eg, diagnostic angiogram) or from a reversible condition, repeat screening assessments to establish eligibility will generally be permitted once, at the discretion of the investigator.
- Eligible participants who have a diagnostic angiogram performed after screening Visit 1 in the absence of undergoing a new PCI may continue screening after the diagnostic angiogram has been performed (Exclusion Criterion 2). If they exceed the 42-day pre-randomization window, the Medical Monitor will decide whether the participant is required to be rescreened and whether screening laboratory evaluations should be repeated. Participants who have a PCI performed between Screening Visit 1 and Randomization Visit 3 may not be rescreened.
- Participants who are excluded based on elevated BP may be rescreened following adequate treatment (Exclusion Criterion 9(c)).

For eligible participants who are rescreened, the rescreen date must also be within the MI window of not more than 365 days since MI.

Rescreened participants should be assigned the same enrollment code as for the initial screening.

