8.3 Adverse Events and Serious Adverse Events

The PI is responsible for ensuring that all staff involved in the study are familiar with the content of this section.

The definitions of an AE or SAE are given in [Appendix B](#).

AEs will be reported by the participant (or, when appropriate, by a caregiver, surrogate, or the participant's legally authorized representative).

The investigator and any designees are responsible for detecting, documenting, and recording events that meet the definition of an AE.

8.3.1 Time Period and Frequency for Collecting Adverse Event and Serious Adverse Event Information

Non-serious AEs will be collected from the time of randomization throughout the treatment period and including the follow-up period.

Serious adverse events will be recorded from the time of signing of the first ICF (either the brief, pre-screening ICF or the full, screening ICF) throughout the treatment period and including the follow-up period.

If the investigator becomes aware of an SAE with a suspected causal relationship to the investigational product that occurs after the end of the clinical study in a participant treated by him or her, the investigator shall, without undue delay, report the SAE to the sponsor.

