4.2.10.7 Adverse events

After having assigned the AEs to the corresponding analysis phase as described in section [3.3.5.1](#), the AEs will be summarized for each treatment group and overall (total will not include placebo subjects). The AEs tables will be based on the as-treated population except the AE by ADA tables which will be based on the Immunogenicity population. Summary tables will include AEs in the on-treatment phase and AEs in the follow-up phase.

Summary tables are listed below.

An overview table containing:

- Number and percentage of subjects with any AEs
- Number and percentage of subjects with any AEs with outcome of death
- Number and percentage of subjects with any SAE (including events with outcome = death)
- Number and percentage of subjects with any AEs leading to discontinuation of treatment
- Number and percentage of subjects with any AEs leading to withdrawal from study

Subjects with multiple events in the same category are counted only once in that category.
Subjects with events in more than 1 category are counted once in each of those categories.

An overview table containing:

- Any AE
- Any AEs with outcome of death
- Any SAE (including events with outcome of death)
- Any AE leading to discontinuation of treatment
- Any AE leading to withdrawal from study

Multiple events in the same category are counted multiple times in that category. Multiple events belonging to more than 1 category are counted multiple times in each of those categories.

The following summary tables will be presented by SOC and PT:

- The number and percentage of subjects with any AEs
- The number of AEs
- The number and percentage of subjects with AEs with outcome of death
- The number of SAEs
- The number and percentage of subjects with SAEs
- The number and percentage of subjects with SAEs, assessed by investigator as possibly related to investigational product
- The number and percentage of subjects with AEs leading to discontinuation
- The number and percentage of subjects with any bleedings (all events from bleeding event form or from adverse event form with SMQ= “Haemorrhages narrow”)
- The number and percentage of subjects with any injection site reactions (all events from ISR form or from adverse event form with HLT= “Injection site reactions”)
- Overall summary of number and percentage of subjects with any AEs by ADA (anti-drug antibody category)
- The number and percentage of subjects by ADA (anti-drug antibody category)

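### A serious adverse event in an enrolled participant who is never dosed, including a serious reaction to the baseline CTA, appears in no planned adverse event table or listing

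*SAP*

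**What the plan says.** On collection, the documents agree. Protocol 8.3.1 states "Serious adverse events will be recorded from the time of signing of the first ICF", whether that is the pre-screening or the full form, and SAP 3.3.5.1 states "Serious adverse events (SAEs) will be collected from time of signature of informed consent". For people who fail screening, Protocol 5.4 requires a minimal record: "Minimal information includes demography, screen failure details, eligibility criteria, and any SAEs". Protocol 8.3.2 adds that each SAE carries a causality assessment against study procedures as well as against the product.

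On the procedure, Protocol 4.1 says that, once eligibility is confirmed, "participants will undergo an echocardiogram and CTA scan before randomization". Protocol Table 6 lists the potential consequences of a CTA scan. They include "Reactions to iodinated contrast" and renal impairment from contrast.

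On reporting, SAP 3.3.5.1 assigns any event that starts before the first dose to the pre-treatment phase. SAP 4.2.10.7 then says "Summary tables will include AEs in the on-treatment phase and AEs in the follow-up phase". It bases the tables on the as-treated population (the Immunogenicity population, a subset, for tables by anti-drug antibody status). Its listing rule is "A listing will be provided for all the AEs regardless of the analysis phases for all subjects included in the as-treated population". The section closes by applying all its analyses to IDMC reports and the final analysis. SAP Table 2 defines as-treated as randomized and having received study treatment. The same table defines an All enrolled subjects population from the first consent form.

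**The concern.** The SAP reports serious events on a narrower set of people than the set on whom they are collected. The people left out are those who consented and were never dosed. Some of them will have had a contrast scan solely because of the study.

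For one kind of event the omission is not neutral. Participants are reassessed for eligibility before dosing on Day 1 (Protocol 5.1), and exclusion criterion 10 includes "Allergy to iodinated contrast" and a history of contrast-induced nephropathy. A serious contrast reaction at the baseline scan can therefore remove the person from the only population in which the event would have been listed.

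At stake is the completeness of the safety account of a study procedure. SAEs are also the only systematic adverse event record for the baseline scan, because collection of non-serious events starts later: at randomization in Protocol 8.3.1, at first dose in SAP 3.3.5.1. Those two start points differ from each other and should be reconciled.

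**Working it through.** No arithmetic applies. The check follows an SAE through the SAP's phase rule, populations and outputs, for three kinds of participant.

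| SAE and participant | AE summary tables | All-phase AE listing |
|---|---|---|
| After the baseline CTA, later dosed | No: pre-treatment phase | Yes |
| After the baseline CTA, never dosed | No: not as-treated | No: not as-treated |
| After the Day 253 CTA, dosed | Yes | Yes |

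The steps for the second row, where the gap lies:

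1. The SAE is collected (Protocol 8.3.1, SAP 3.3.5.1). Protocol Table 3 schedules SAE assessment at the baseline imaging visit.
2. The person receives no dose, so is outside the as-treated population (SAP Table 2). This is so whether or not the person was randomized.
3. All adverse event tables in SAP 4.2.10.7 use the as-treated population or its Immunogenicity subset. The key subject information tables for deaths and SAEs are among them.
4. The listing that ignores phase does not ignore population, so it does not recover the event.
5. SAP 4.2.1 does use All enrolled subjects, for the disposition table, the disposition listing and the listings of exclusions from each population. These give a disposition term or a reason for exclusion. They do not give the event, its seriousness or its causality.
6. SAP 4.2.11 also uses all enrolled subjects, but only for outputs on the COVID-19 and global/country situation.

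For the third row, a participant on schedule has the last dose on Day 225, and 225 + 28 = 253. An event on Day 253 is thus on-treatment and a later one falls in follow-up (SAP Table 4). Both phases are tabulated.

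Procedure causality is collected, but no planned table uses it. The only related-SAE table in SAP 4.2.10.7 concerns the investigational product.

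Enrolled, undosed people are not hypothetical. SAP 6 records two subjects randomized in error who took no dose and are classed as screen failures. It does not say whether they were scanned. Inclusion criterion 6 also needs an evaluable scan with quantifiable non-calcified plaque, so a person can be scanned and then fail.

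Parts of SAP 4.2.10 on exploratory endpoints are redacted and could not be checked. Section 4.2.10.7 itself is not redacted. The IDMC charter is a separate document and was not available.

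**The case against.** The best defence is that the SAP follows the protocol's stated scope. The safety objective compares MEDI6570 with placebo, adverse events are an endpoint during the intervention and follow-up periods (Protocol Table 7), and Protocol 9.4.3 names the as-treated population for safety analyses. That stands: as-treated is a suitable set for the drug comparison and should stay. It does not explain why serious events collected outside that set, and kept for screen failures so that these are reported transparently, have no listing at all.

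A second defence is that every SAE goes into the eCRF and reaches the sponsor within 24 hours (Protocol 8.3.7). This also stands, and confines the point to planned study outputs. It is not a failure of case-level safety oversight.

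Four stronger readings are tempting, and the documents do not support them:

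- That SAEs are collected from consent because of the CTA. No section gives that reason. Collection starts at pre-screening, before any scan, and only participants who meet eligibility are scanned (Protocol Table 3).
- That the person vanishes from every output. Disposition and exclusion outputs can still show the person, without the event.
- That the report would show almost no baseline-scan harm whatever the true rate. Events that do not prevent dosing are listed, and events after the Day 253 scan are tabulated. The selective loss applies to events that stop entry.
- That the number of people affected can be estimated. The documents give no loss rate between scan and dosing, and a count of people scanned would not be a count of events.

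**Conclusion.** The point holds as a gap in reporting. An SAE or death in an enrolled, never-dosed participant appears in no adverse event output, either at final analysis or in the IDMC outputs that the SAP defines. For contrast allergy and contrast nephropathy at the baseline scan, the loss is linked to the event itself. For dosed participants the gap is smaller: a pre-treatment SAE is listed but not tabulated.

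Its size in events is unknown and may be zero. The conclusion rests on the visible text of the SAP and assumes that neither the IDMC charter nor the redacted text adds such an output. It changes no efficacy result and no comparison of MEDI6570 with placebo, and it concerns reporting only, not clinical management.

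**What to change.** In SAP 4.2.10.7, add a listing of all SAEs and deaths from first consent on the All enrolled subjects population. Flag each person as dosed or not dosed, show the causality to study procedure, and produce the listing for IDMC reports and the final analysis. Keep the as-treated population for the treatment comparison.

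If a count is also given, use all participants who had a baseline CTA as the denominator. Restrict the numerator to SAEs with onset on or after that scan and before the first dose, or at any time after the scan if the person was never dosed. Without that restriction the numerator would take in events from before the scan and from people never scanned: on the Protocol Table 3 windows, first consent can precede the scan by up to 83 days (Day -84 to Day -1).

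The cost is SAP wording, one listing and, optionally, one small count, all from data already collected. No new assessment is needed.
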